### ***Imputing Data***

After excluding individuals based on the above criteria, we will impute any missing data in our variables of interest (pre- and post-intervention likelihood of future NSSI; pre- and post-intervention desire for future NSSI; past 3-month frequency of NSSI at pre-intervention and follow-up). To do this, we will execute an expectation-maximization and bootstrapping algorithm via the Amelia II package in R (Honaker, King, & Blackwell, 2011; <https://cran.r-project.org/web/packages/Amelia/Amelia.pdf>). All variables from the corresponding statistical model (i.e. hypothesis tests 1 - 3) will be included in the algorithm used to create the imputed data for that test: (a) baseline values for the outcome—likelihood of NSSI, desire for NSSI, or past 3-month frequency of NSSI, (b) follow-up values for the outcome, and (c) condition assignment, as well as (d) other baseline variables that are likely associated with each outcome variable (for **past 3-month frequency of NSSI at follow-up**: lifetime history of NSSI (y/n), past-month frequency of NSSI, past-year frequency of NSSI, and lifetime frequency of NSSI at baseline; for **likelihood of NSSI post-intervention**: all of these same variables plus past 3-month frequency of NSSI at baseline; for **past 3-month frequency of SI at follow-up**: lifetime history of SI (y/n), past-month frequency of SI, past 3-month frequency of SI, past-year frequency of SI, and lifetime frequency of SI at baseline). Together, these variables (a - d) will be used to create the imputed datasets for each of our three hypotheses.

The number of imputed datasets we create will equal the percentage of missing data for each of our three outcome variables (post-intervention likelihood of NSSI, post-intervention desire for future NSSI, past 3-month frequency at follow-up), rounded up to the next integer value. For example, we will create 7 imputed datasets to test hypothesis 1 if 6.2% of the data for the post-intervention likelihood of NSSI outcome variable is missing. We will create 8 imputed datasets to test hypothesis 2 if 7.6% of the data for the post-intervention desire for future NSSI outcome variable is missing.

Lastly, we will run all of our confirmatory tests for hypothesis 1 - 3 as outlined in this pre-registration, within the original study data (i.e. removing/disregarding missing data in the original dataset and ultimately using non-imputed data). We will report the results in our supplementary materials for the present study. If main results/interpretations differ between analyses run within imputed vs. non-imputed data, we will report and discuss our paper's discussion.

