### ***Secondary Dependent Variables***

**Likelihood of Future NSSI.** Likelihood of future NSSI will be measured immediately pre- and post-intervention. We will evaluate self-reported likelihood of future non-suicidal self-injury immediately post-intervention—comparing participants in the Project SAVE SSI versus supportive therapy SSI control conditions, and controlling for pre-intervention likelihood score. An item from the Self-Injurious Thoughts and Behaviors Interview-R (Fox et al., 2020) will assess participants’ beliefs about the likelihood of future non-suicidal self injury on a 5-point Likert Scale (range = 0 to 4; 0 = “not at all”; 4 = “extremely”).

**SI Frequency in the Past 3 Months.** We will compare past 3-month SI frequency at 3-month follow-up—for participants assigned to the Project SAVE SSI versus supportive therapy SSI (i.e. control condition). At pre-intervention and 3-month follow-up time points, participants will indicate “how many days did they have thoughts about killing themselves for more than a few minutes” in the past 3 months in an open-response text box. Notably, in the present study’s survey flow, this question is displayed following display logic—such that participants endorsing zero history of SI in the past 3 months (via a previous question) skip to the end of the question block and are not prompted to answer our frequency outcome question. For these individuals, we will impute a past 3-month frequency value equal to 0 (as they have endorsed zero SI in the previous 3 months in the earlier question). More information about how we will handle very large numbers (i.e. outliers) for this outcome is reported below (see “Outliers and Exclusions” section; “Winsorizing Outliers” subsection).

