#### **How many and which conditions will participants be assigned to? (optional)**

Participants will be randomly assigned to 1 of 2 possible conditions, per a 1:1 allocation ratio: (1) an online, active control group program encouraging feelings disclosure (i.e. supportive therapy SSI), or (2) an online program targeting behaviors and thoughts relating to self-injury (i.e. Project “SAVE”—Stop Adolescent Violence Everywhere—SSI). Random assignment to condition will be conducted in a triple-masked manner. Therefore, participants will be masked to whether they received active treatment and investigators will be masked to which condition the participant is randomized to—as the randomization occurs automatically within the survey. Additionally, as the primary and secondary outcomes are self-report measures, we will not be utilizing an outcomes assessor (e.g. a clinical interviewer). Participants will be informed of their condition assignment following their completion of the full study protocol by debriefing form. Investigators will be informed of participant condition after data collection is complete (i.e. the data analysis phase).

**Supportive Therapy (“Share Your Feelings”) SSI** (Schleider & Weisz, 2019; see <https://osf.io/u4axs/>) is a ~30-minute, self-administered, web-based program that uses components of supportive therapy to encourage feelings sharing. Like Project SAVE, this SSI takes approximately 30 minutes to complete and is self-administered online. The supportive therapy SSI encourages participants in the control group to identify and express their feelings by (1) explaining why sharing feelings is natural, important, and helpful and (2) including testimonials from teens who have shared their feelings with close others.

**Project SAVE (“Stop Adolescent Violence Everywhere”) SSI** is a ~30-minute, self-administered, web-based program that uses components of cognitive behavior therapy and dialectical behavior therapy designed to decrease self-injurious behaviors in youth. The SSI’s content is designed to maximize relevance for youth engaging in self-injurious behaviors by

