### ***Type 1 Exclusions***

Type 1 exclusions are exclusions that can be automated and do not require consensus among investigators. A research team member who will not be involved with conducting the primary study analyses will use type 1 exclusions to determine when participant recruitment is complete. Recruitment for the present study will end once 500 participants have been randomized *who pass all type 1 exclusions tests* (i.e. are still eligible for inclusion after excluding for type 1 criteria; see our section on sample size for more details).

Here, we will exclude participants that fail to meet the following study inclusion criteria:

- Must be 13 - 16 years old at the time of the baseline survey
- Must report comfort reading and writing in English

- Must endorse no learning disability, visual impairment, or other difficulty that makes it difficult to answer questions on a computer
- Must have access to a laptop or smartphone with internet access
- Must endorse purposefully hurting self without wanting to die within the past month
- Must endorse *either* “I do not like myself” or “I hate myself” on CDI-II item 7 in a screener survey

Here, we will exclude the following participants based on failure to meet the following quality check criteria:

- Participants who exit the study *prior* to condition randomization for our listed analyses (note: the present study will use an intention-to-treat approach, where every participant who was randomized to a study condition—and who is not excluded for one of the specific reasons outlined in this section—will be included in our analyses)

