### ***Winsorizing Outliers***

We will winsorize outliers in our two count variables of interest (past 3-month frequency of NSSI at pre-intervention and follow-up) before running tests for hypothesis 2 and 3. Outliers will be defined as values above the 95th percentile for the variable in question, calculated using the Winsorize() function in the DescTools package in R (Singnorell et al., 2020, <https://cran.r-project.org/web/packages/DescTools/DescTools.pdf>).

[project.org/web/packages/DescTools/DescTools.pdf](https://project.org/web/packages/DescTools/DescTools.pdf)); flagged outliers will be replaced with the 95th percentile value.

**How many observations will be collected or what will determine the sample size? No need to justify decision, but be precise about exactly how the number will be determined. (optional)**

The final sample size for *collected* data will be  $N = 500$  randomized participants (250 per condition) who meet our type 1 inclusion criteria (i.e. who are not excluded by type 1 exclusion criteria outlined in the above section). The total number of participants who provide *usable* data will then be determined by the number of participants who meet our type 2 inclusion criteria (i.e. who are not excluded by type 2 exclusion criteria outlined above). Therefore, the present study will have a maximum of 500 participants, with a final sample size determined by the number of participants meeting our type 2 inclusion criteria specified above.

**Other. Anything else you would like to pre-register? (e.g., secondary analyses, variables collected for exploratory purposes, unusual analyses planned?) (optional)**

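### Hypothesis 1 (secondary outcome): youths who leave during the SSI are imputed with the responders' treatment difference, so the effect size reported as intention-to-treat may be too large, and the only check runs only when dropout differs between arms

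*Combined protocol and SAP*

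**What the plan says.** All places are in the Combined protocol and SAP.

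- **Timing of the outcome** (Secondary Dependent Variables): "Likelihood of future NSSI will be measured immediately pre- and post-intervention". No later assessment of this item enters hypothesis 1 (H1).
- **Point of randomisation** (section on conditions): investigators are masked "as the randomization occurs automatically within the survey". Both SSIs take about 30 minutes, so a youth can be randomised and then leave partway.
- **Analysis principle** (Type 1 Exclusions): "the present study will use an intention-to-treat approach, where every participant who was randomized to a study condition" is analysed unless excluded for a listed reason.
- **Imputation** (Imputing Data): "we will impute any missing data in our variables of interest (pre- and post-intervention likelihood of future NSSI". The H1 model uses the baseline and post-intervention values of the item, condition, and baseline NSSI history. No variable marks leaving the SSI.
- **Non-imputed rerun** (end of Imputing Data): H1 to H3 are repeated after "removing/disregarding missing data in the original dataset and ultimately using non-imputed data".
- **Missing-not-at-random analysis** (Testing for Differential Dropout): all dropouts are given the 25th, then the 75th, percentile of residual change. This is done only if a Z-test finds dropout different between conditions at p < .05. The same section acknowledges that imputing from completers can miss worsening among dropouts.
- **SSI-completer analysis** (Treatment Effects Among SSI Completers): covers the primary 3-month outcome only.

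**The concern.** The H1 outcome differs from the 3-month outcomes. A youth who quits the SSI can still answer at 3 months, but very probably never reaches the post-intervention item. The imputation model must therefore learn its condition coefficient from youths who answered, and it applies that coefficient to those who left. In effect, SAVE youths who quit are credited with the benefit seen in those who stayed.

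The two safeguards do not reach this. The non-imputed rerun uses the same responders, so its agreement with the imputed result shows nothing about stoppers. The missing-not-at-random analysis depends on a difference in dropout between arms, whereas the dilution depends on how many SAVE youths stop. If 20% stop in each arm, the trigger has nothing to detect and the dilution is fully present.

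What is at stake is the size of the H1 effect and the population it describes.

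**Working it through.** **Inputs from the plan.** Allocation is "per a 1:1 allocation ratio", with 500 "randomized participants (250 per condition) who meet our type 1 inclusion criteria". H1 is tested on the condition coefficient, adjusted for baseline, at p < .05 after false discovery rate correction. The only H1 missingness figure is an illustrative 6.2%. **Not given:** an expected stopping rate, an H1 effect size, an SD or a power calculation.

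**1. The plan's own figure.** The number of imputed datasets is the percentage missing, rounded up: 6.2 gives 7, and 7.6 gives 8. Both match the plan.

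**2. Algebra.** Let Δ be the effect in finishers, d the share stopping before the item (equal in both arms), and r the fraction of Δ that stoppers gain.

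- Effect in all randomised = (1 − d)Δ + d·rΔ = Δ[1 − d(1 − r)].
- Imputation from responders returns Δ.
- Ratio of reported to all-randomised effect = 1/[1 − d(1 − r)].

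With r = 0:

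- d = 6.2%: 1/0.938 = 1.066, about 7% too large
- d = 10%: 1/0.90 = 1.11, 11%
- d = 20%: 1/0.80 = 1.25, 25%
- d = 30%: 1/0.70 = 1.43, 43%

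With r = 0.5 and d = 20%: 1/0.90 = 1.11. With r = 1 the ratio is 1 at any d.

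**3. Simulation of the planned analysis.** It used 250 per arm, 600 replicates, bootstrap regression imputation with the plan's number of datasets, then baseline-adjusted regression. Assumed: a finisher effect of −0.30 points and equal stopping. The outcome is continuous except in the last row.

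| Stopping; effect in stoppers | All randomised | Non-imputed | Imputed | Percentile analysis (25th / 75th) |
|---|---|---|---|---|
| 6.2%; 0 | −0.283 | −0.301 | −0.301 | −0.282 / −0.282 |
| 10%; 0 | −0.270 | −0.302 | −0.301 | −0.271 / −0.271 |
| 20%; 0 | −0.240 | −0.300 | −0.299 | −0.239 / −0.239 |
| 30%; 0 | −0.208 | −0.300 | −0.300 | −0.209 / −0.210 |
| 20%; −0.30 | −0.297 | −0.293 | −0.294 | −0.234 / −0.235 |
| 20%; 0, rounded to 0–4 | −0.225 | −0.279 | −0.279 | −0.223 / −0.223 |

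Imputed and non-imputed estimates agree within 0.002 points in every row, whether or not they are right for all randomised youths. The percentile analysis, with one common value for both arms, recovers the all-randomised effect when stoppers gain nothing. It understates that effect when they gain equally (fifth row).

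**4. The trigger.** With equal stopping, the dropout test is significant only at its 5% false-positive rate. For a true 5-point difference at 250 per arm, its power is 57% (5% vs 10%), 39% (10% vs 15%), 31% (15% vs 20%) and 27% (20% vs 25%).

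**5. The test of no effect.** With equal stopping and no effect in anyone (SD 1, baseline correlation about 0.6, both assumed), the planned analysis rejected in 5.1%, 4.9% and 5.7% of simulated trials at 10%, 20% and 30% stopping. A separate set of runs gave 5 to 7%.

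**The case against.** The strongest reply has five parts.

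- **The H1 decision is unaffected.** When stoppers gain nothing, the all-randomised effect is (1 − d)Δ, which is zero exactly when Δ is zero. This stands. A reader might infer that H1 significance, or the false discovery rate family it belongs to, is compromised; step 5 shows that it is not in this scenario.
- **The missing outcome is inferred.** A reader might take it as documented that no stopper is ever observed on H1. No sentence says so. A dropout is anyone who did not get through all post-intervention sections, which can include youths who finished the SSI and answered the item. This stands, hence the wording very probably.
- **Some stoppers may never reach imputation.** Type 2 Exclusions removes responses of three words or fewer to writing prompts, and imputation follows exclusion. Whether blanks count is not settled. This may reduce the number imputed; it does not change how the rest are handled.
- **The size is hypothetical.** It depends on stoppers gaining less and on a stopping rate the plan does not give. This stands, and the result is therefore shown as a range that includes zero.
- **The plan already recognises the problem.** It does, in Testing for Differential Dropout, but it makes the remedy conditional on a test that cannot see equal stopping. This part does not answer the point.

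**Conclusion.** The point holds for H1, as a matter of effect size and description. The main H1 estimate assumes that youths who leave the SSI respond like finishers with the same baseline and condition. Nothing in the H1 data can test that, and no analysis that is certain to be run relaxes it. If stoppers gain nothing and stopping is equal, the reported effect is too large by about 7% to 43% for stopping between 6.2% and 30%. If they gain equally, the excess is nil. That stoppers gain less is plausible for youths who did not receive the full program, but it is an assumption. The factor applies to a mean difference; under the plan's ordinal fallback it is only a guide.

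A reader might go further and infer that the H1 result is known to be inflated, or that the primary outcome has the same fault. The documents support neither. They contain no stopping rate and no information on benefit in stoppers, and an SSI stopper can still answer the 3-month questions. H1 is secondary, so this is a cheap improvement and not a flaw in the trial's main claim.

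**What to change.** 1. For H1, remove the condition in Testing for Differential Dropout. Always run the 25th/75th percentile residual-change imputation and report it beside the main result.
2. State that each percentile is one value applied in both arms, so that stoppers receive no arm difference. The plan does not say this now.
3. Describe the main H1 estimate as assuming that stoppers respond like finishers with the same baseline.
4. Compare estimates and intervals. Do not tie the wording of the conclusion to whether significance survives.

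Drawing SAVE stoppers from the control-arm model is a less suitable alternative. The control is itself an active SSI and its model would be fitted on control responders, so stoppers would be credited with a finished control program. The usual pooled standard error would also be too wide: with an assumed finisher effect of −0.2, it was 0.079 against a true spread of 0.065 at 20% stopping. Significance could then be lost through the variance formula alone.

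Two limits should be stated. The percentile analysis understates the effect if stoppers do benefit. With unequal stopping its range need not contain the truth: with 20% stopping in SAVE, 15% in control, and stoppers 0.5 points worse in both arms, the truth was −0.210 and the range −0.271 to −0.217.

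Cost: a few sentences in the plan, one extra analysis, and a possibly smaller reported H1 effect. No new data are needed. The plan states that none had been collected, so the change can be registered in advance.

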**Discrimination.** The Expanded Everyday Discrimination Scale will be measured pre-intervention to gauge the levels of relatively minor, every-day, chronic discrimination experienced by participants. The original scale (Williams et al., 1997) asks participants, "In your day-to-day life, how often do any of the following things happen to you?" for 9 items (e.g. "you are treated with less courtesy than other people are") on a 5-point Likert scale (1= "never"; 6 = "almost every day"). These items assess the participant's observations about how others treat and act around them on a daily basis. The expanded version of this scale includes a 10th item, "You are followed around in stores." Scores on the Expanded Everyday Discrimination Scale range from 10-60, with higher scores indicating higher levels of chronic discrimination experienced by participants. Respondents are also asked to identify what they believe to be the main reason(s) for these experiences (e.g. gender, race, age, etc.).

[https://scholar.harvard.edu/files/davidrwilliams/files/measuring\\_discrimination\\_resource\\_june\\_2016.pdf](https://scholar.harvard.edu/files/davidrwilliams/files/measuring_discrimination_resource_june_2016.pdf)

**Self Hate.** Self-hate will be assessed immediately pre-intervention, post-intervention, and follow-up using the Self Hate Scale (Turnell, Fassnacht, Batterham, Calear, & Kyrios, 2019), which is measured on a 7- point Likert scale. The Self Hate Scale asks participants to "Rate how true each of the following statements are for you right now, in this moment" for 7 items (e.g. "I hate myself"; 1 = "not at all true for me"; 7 = "very true for me"). Scores on the Self Hate Scale range from 7-49, with higher scores indicating higher levels of self hate.

<https://www.sciencedirect.com/science/article/abs/pii/S0165032718313144>

**Disordered Eating.** Disordered eating behaviors will be measured at pre-intervention and 3-month follow-up using The Dietary Restriction Screener (DRS-2; Haynos & Fruzzetti, 2015). The DRS-2 is a 9-item measure evaluating restrictive eating, bingeing, and purging behaviors in participants. 6 items ask participants whether or not they have engaged in restrictive eating, bingeing, or purging behaviors in the past year or in the past 3 months (0 = no; 1 = yes). The other 3 items assess the frequency of these behaviors over the past 28 days.

<https://link.springer.com/article/10.1007/s40519-014-0161-0>

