**Specify exactly which analyses you will conduct to examine the main question/hypothesis. (optional)**

***Testing for Differential Dropout***

First, we will test for differential dropout by study condition. To do this, we will use Z-tests of differential proportions where we compare the proportion of people who drop out before completing the study (Y or N) as a function of treatment condition (0 = control group SSI, 1 = Project SAVE SSI). We will run two tests evaluating differential dropout: (1) measuring dropout prior to finishing our post-intervention questions, and (2) measuring dropout prior to finishing our 3-month follow-up questions. To be considered a study “completer” for the post-intervention questions, a participant must have made it through all post-intervention survey sections (i.e. all sections but “final block” section that presents information for study logistics). To be considered a study “completer” for the 3-month follow-up questions, a participant must have made it through all follow-up survey sections (i.e. all sections but “final block” section that presents information for study logistics).

If the *p* value is greater than .05 we will assume dropout was not dependent on condition assignment and can proceed with interpreting the effects of intervention assignment (i.e. proceed with the between-group analyses exactly as described below, starting in the section labeled “Hypothesis 1”).

If the *p* value for this test is less than .05 we will conclude that dropout was dependent on condition assignment, and we will take the following steps to improve the interpretability of our results. Unequal dropout between treatment groups can introduce bias in trial results; however, this is not always the case (Bell, Kenward, Fairclough, & Horton, 2013; <https://doi.org/10.1136/bmj.e8668>). One major concern is that, if data are *not missing at random*, systematic differences may exist between “dropouts” and “completers” that cannot be corrected for, limiting the interpretability of our results. For example, if more control condition participants experienced a worsening of clinical symptoms and dropped out before completing follow-up measures, this worsening of symptoms would not be captured by completers’ data (or by data imputed based on the available completers’ data). Thus, should unequal dropout exist

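### The imputation models for the 3-month NSSI and SI counts leave out two post-session measures already collected, which exposes the treatment effect to avoidable bias if reasons for dropout differ by arm

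*Combined protocol and SAP*

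**What the plan says.** All references are to the combined protocol and SAP.

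- **Imputing Data** sets up imputation test by test: the variables of each model "will be included in the algorithm used to create the imputed data for that test". The inputs are (a) the baseline outcome, (b) its follow-up value, (c) condition and (d) "other baseline variables that are likely associated with each outcome variable". For 3-month NSSI, list (d) is "lifetime history of NSSI (y/n), past-month frequency of NSSI, past-year frequency of NSSI, and lifetime frequency of NSSI at baseline". The SI list is of the same kind. No post-session measure appears in either.
- **Secondary Dependent Variables**: "Likelihood of future NSSI will be measured immediately pre- and post-intervention".
- **All Other Variables**: "Self-hate will be assessed immediately pre-intervention, post-intervention, and follow-up using the Self Hate Scale".
- **Testing for Differential Dropout** tests loss before the end of the post-intervention questions separately from loss before the end of the 3-month questions. It runs a percentile-based sensitivity analysis only if dropout differs by arm at p < .05.
- **Type 1 Exclusions**, on eligibility: "Must endorse purposefully hurting self without wanting to die within the past month".

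**The concern.** A youth who completes the post-survey and is then lost at 3 months has left two recent, relevant measurements. They are the last observations before the loss, and they post-date the session, so they can carry some of the response to it. An imputation that conditions only on arm and baseline assumes that, given those, dropouts resemble completers. Including the markers weakens that assumption to one conditional on them as well.

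The plan recognises the general danger, giving as an example the case "if more control condition participants experienced a worsening of clinical symptoms and dropped out before completing follow-up measures". Any part of such worsening already visible after the session could be brought into the imputation. At stake is the primary between-arm comparison. The existing safeguards do not fill the gap: the sensitivity analysis responds to unequal dropout totals, not to unequal reasons for dropout, and the supplementary analysis of non-imputed data ignores the same markers. Agreement between imputed and non-imputed results would therefore be weak reassurance.

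**Working it through.** **Inputs from the documents.** 500 randomised, 1:1, 250 per condition (2 × 250 = 500). The number of imputations is the percentage missing, rounded up; the plan's examples reproduce (6.2 gives 7, 7.6 gives 8). No dropout rate, marker-outcome correlation or treatment effect is given, so those below are assumptions.

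**Step 1: bias when dropout depends on the marker in the control arm only.** Simulation of 3,000 trials of 500. T is arm (1 = SAVE), B a standard normal baseline, P the post-session marker, Y the 3-month outcome on a continuous scale:

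- P = 0.5B − 0.3T + noise; Y = 0.5B + sP − 0.05T + noise
- True effect = −0.05 − 0.3s, which is −0.17 for s = 0.4 and −0.11 for s = 0.2
- Logit of dropout = −1 + 0.8P in control and −1 in SAVE, where 1/(1 + e) = 27%; control dropout comes to 29% to 30%

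The baseline-only column is the arm coefficient from observed cases given T and B. It stands in for imputation from arm and baseline, and assumes that the extra history items carry nothing more about P. The last column imputes Y with P added and every dropout's P observed.

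| Residual SD | s | Full data | Baseline-only | Marker added | Share lost |
|---|---|---|---|---|---|
| about 0.87 | 0.4 | −0.167 | −0.105 | −0.167 | 0.062/0.167 = 37% |
| about 0.87 | 0.2 | −0.109 | −0.077 | −0.109 | 0.032/0.109 = 29% |
| 1 | 0.4 | −0.173 | −0.089 | −0.172 | 0.084/0.173 = 49% |
| 1 | 0.2 | −0.109 | −0.068 | −0.109 | 0.041/0.109 = 38% |

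An SD of 0.87 gives the marker unit variance within arm (0.25 + 0.75 = 1). With SD 1, the planned z-test for differential dropout was significant in only about 11% of trials.

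**Step 2: the same dependence in both arms.** With the dropout model −1 + 0.8P in both arms, the loss is about 5% (4% to 8% across runs).

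**Step 3: large-sample check with dropout totals forced equal.** Here r is the marker-outcome correlation and d the dropout fraction; there is no baseline covariate. Bias without the marker, in SD units:

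| Dropout depends on marker | r = 0.3, d = 20% | r = 0.5, d = 40% |
|---|---|---|
| equally in both arms | about 0 | about 0 |
| in control only | 0.05 | 0.17 |
| in opposite directions by arm | 0.11 | 0.33 |

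With the marker included, and observed for everyone, the bias is about 0 in every cell. Equal totals therefore do not rule the problem out.

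**Step 4: participants who leave before the post-survey have no marker.** In the model with s = 0.4 and SD 1, the true effect is −0.17 and the baseline-only estimate −0.085, a gap of 0.085. If half the dropouts leave before the post-survey, the estimate with the marker is −0.133, so 0.048/0.085 = 56% of the gap is recovered. If 80% do, it is −0.108, and 0.023/0.085 = 27% is recovered.

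**Step 5: precision.** The variance ratio with versus without the marker is 1 − r²d. For r = 0.3, d = 30%: 1 − 0.09 × 0.30 = 0.973. For r = 0.5, d = 40%: 1 − 0.25 × 0.40 = 0.90. The gain is small; bias is the reason to act.

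**Step 6: the predictor lists.** Eligibility requires past-month NSSI, so a yes/no lifetime history of NSSI is yes for every eligible participant. Its variance is zero and it contributes nothing. Item (a) glosses the outcomes as "likelihood of NSSI, desire for NSSI, or past 3-month frequency of NSSI, (b) follow-up values for the outcome, and (c) condition assignment", which does not name SI. Baseline 3-month SI is named in list (d), and enters again only by implication, as the baseline value of the outcome and the Hypothesis 2 covariate.

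**The case against.** The strongest reply is that material bias needs dropout to relate to the marker differently by arm, and nothing in the documents indicates such a pattern. Step 2 supports this. A reader might infer that imputation from baseline is valid only if dropout is unrelated to the response to the session, and biased otherwise. The documents do not support that, and the calculation contradicts it: a shared dependence costs about 5%.

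A reader might also infer that the markers restore the true effect. That result follows from making dropout depend on nothing else and observing every dropout's marker. Step 4 shows partial recovery, and a measure taken straight after a session of about 30 minutes cannot see worsening in the following months. That later worsening is a missing-not-at-random problem, which the plan addresses only if the dropout test is significant.

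The scale is also a fair criticism. The planned outcomes are winsorized counts in Poisson-family models, so the percentages do not transfer directly. The shift of about 0.06 to 0.085 is smaller than one standard error (about 0.11). This limits the alarm, but a systematic shift toward no effect is still worth preventing when it costs nothing.

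The closing sentence on items (a) to (d) could be read as one joint model, which would bring in post-session likelihood. The wording for that test and the outcome-specific number of imputations point to separate models, and self-hate is absent on either reading.

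Two further inferences go too far. Baseline 3-month SI is not listed twice: it is named once, so simply deleting it would remove its only explicit mention. And the constant NSSI item is housekeeping; an analyst would drop the column and no estimate would change.

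**Conclusion.** The concern holds as a specific, inexpensive improvement to the imputation of the primary outcome and of SI frequency. The plan leaves out two relevant post-session measures that it already collects, and so relies on a stronger missing-at-random assumption than it needs.

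The possible loss is roughly 30% to 50% of the effect if dropout depends on the marker in the control arm only, with about 28% missing and a continuous outcome. It is about 5% if the dependence is the same in both arms. Both figures rest on assumed dropout, marker-outcome association and effect size. The omission does not show that the 3-month effect will be biased. It shows that one plausible route to bias is left open, and that the planned dropout test would usually miss it.

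**What to change.** In Imputing Data, add pre- and post-intervention likelihood of future NSSI and pre- and post-intervention Self Hate scores as auxiliary variables in the imputation models for 3-month NSSI and 3-month SI. State that the post-session values stay out of the outcome regressions: treatment may affect them, and adjusting for them would change the effect being estimated.

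As a minor tidy-up, drop the yes/no lifetime history of NSSI from the NSSI and likelihood lists. Name SI frequency in item (a) first, and only then remove baseline 3-month SI from list (d), so that it enters once.

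The cost is wording and slightly larger imputation models. The variables are already scheduled and the plan states that no data have been collected, so the change can be made before any results are seen. Participants who leave before the post-survey gain little, and worsening after the session stays out of reach.
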